**Data collection procedure.**

The clinical data of the exposed cohort corresponding to the patients operated on during the year 2020 will be extracted from the data collection records that the medical directorate manages for the follow-up of these patients and the report to the National Hip Fracture Registry.

The clinical and care data of the unexposed cohort of patients who will undergo surgery in 2021 will be collected by the trauma team during scheduled patient follow-up visits and by the patient or the patient's caregiver using a mobile application. This data will be recorded and the PI will be responsible for the safekeeping and processing of the data in accordance with current legislation.

The present study is part of a global project to monitor the cohort of patients with hip fractures operated on at the HSJD. This project is a "*real world data*" study in which all the variables of routine practice are collected through a technological application that allows the clinical situation of the patient to be known in real time. The information will be collected through the Caaring® app, developed by Persei Vivarium, with the specific programme for the care of hip fracture patients.

The patient, or the responsible person in patients with cognitive impairment, will receive instructions on how to download the mobile application to their device from an open repository of publicly available mobile applications. The patient will be provided with an access code in which no recognisable data is included. This code allows connection to the questionnaires and information provided by the HSJD trauma service. Only the PI will have a system of correlation between the code and the patient's personal data, and will be responsible for its safekeeping.

The app has two different profiles (doctor, patient), with the researchers being able to enter the data from the face-to-face assessments and the patient or main caregiver the follow-up data from home.

The specialist who monitors the patient has a control panel on the web-app, where he/she has access to risk alerts generated by the system based on the data collected and the clinical rules established for this purpose.

Content of the tool:

The tool has two types of content:

- Questionnaires for the collection of data on the clinical, functional and quality of life evolution of the patient as shown in table III.

**Table III. Summary of variables, assessment instruments and collection period**

Variable	Questionnaire	Time of administration
March Capacity	RNFC scale	Entry, at 6 weeks, 4 months and 1 year.
	The walking capacity assessment scale (mFAC).	Entry, at 6 weeks, 4 months and 1 year.
Physical capacity	Barthel Index	At 6 weeks, 4 months and 1 year.
	Oxford Hip Score Scale	At the 1st, 3rd, 6th and 12th month.
Sarcopenia	SARC-F Scale	At 6 weeks, 4 months and 1 year.
Adverse Events	STRATIFY scale	At 6 weeks, 4 months and 1 year.
	Medical complications (ad hoc questionnaires)	At 6 weeks, 4 months and 1 year.
Quality of life	Questionnaire EQ-5D-5L	At the 1st, 3rd, 6th and 12th month.

- The functional recovery programme designed and implemented as standard practice from 1 January 2021. This programme consists of a series of presentations and videos, in simple language with information and recommendations. It will provide answers to patients' most frequently asked questions and will also allow patients to receive reminders regarding their care (recommended exercises, precautions to take in certain circumstances, alerts, etc.).

It is the clinician and the patient, or family member if applicable, who enters the data directly into the application, prior to accepting the legal clauses to that effect.

The study variables collected in the project are included among the clinical variables included in the orthogeriatric protocol for the care of hip fracture patients at the HSJD. In order to analyse those established for this study, the variables will be extracted from the data collection platform, the PI being responsible for the storage and processing of the data in accordance with current legislation.

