## Sampling

**Sample and procedure for inclusion of patients in the unexposed cohort.**

In order to carry out an analysis of the new care model (functional recovery programme and patient follow-up through a digital application), the entire simple universe will be included, a complete cohort analysis, with follow-up at 1, 3, 6 and 12 months using a digital toolFollow-up will be carried out at 6 weeks, 4 months and 12 after discharge according to the protocol of the orthogeriatrics unit.

The patient will be given instructions on how to download the application to their mobile device. The application is available in the open repository of mobile applications for public use. Once the app is installed, the patient will be provided with a personal access code that does not include recognisable personal data. This code will be used to connect to the therapeutic plan and to the questionnaires provided by the patient when registering with the Traumatology Service. Only the principal investigator (PI) will have a system of correlation between the code and the patient's personal data, be responsible for its safekeeping.

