#### **Variables**

In the two groups that form part of this study, different variables specified in the database adapted from the National Hip Registry and the *International Fragility Fracture Network*, of which the HSJD is a member, will be collected.

Until now, data collection and patient follow-up was completed after one month and the data was transferred annually to the National Hip Fracture Register. In the new model proposed by orthogeriatrics unit of the HSJD, patients will be followed up in person at one and a half months, four months and one year, and at discharge, one month after discharge, three months, six months and one year, by means of a digital application.

The variables to be collected are described below:

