30-39: Mild to moderate impact.

40-48: Satisfactory condition.

This scale is administered at 1, 3, 6 and 12 months.

- **Monitoring of adverse events.**

During the follow-up period, information will be collected on variables derived from post-surgical and medical complications, and falls risk monitoring will be performed.

- **Adverse events. Catalogued in:**

0= Fall.

- 1= Pneumonia.
- 2= New fractures.
- 3= Dementia.
- 4= Acute Myocardial Infarction.
- 5= Pulmonary embolism.
- 6=Deep vein thrombosis.
- 7= Death.

This scale is administered at 6 weeks, 4 months and 1 year.

- **Falls risk scale: STRATIFY scale.**

It can predict which patients are at high risk of falls, with sensitivity values of 92% and specificity of 68% for the elderly population (46).

The total score of the STRATIFY scale is obtained based on the sum of the answers to the five questions, which can take values between zero and five. A score of 0 corresponds to a risk considered low, equal to 1 corresponds to a moderate risk and, finally, greater than or equal to 2 corresponds to a high risk (47).

Question:

1. Patient hospitalised for falls or with episodes of falls during hospitalisation?
2. Restless patient?
3. Are you a patient with visual impairment that affects your daily activity?
4. Patient with a frequent need to use the toilet?
5. Does the patient have a transfer or mobility score of 3 or 4?

However, in the last question, the score is obtained by combining two answers from the modified Barthel index in relation to, respectively, the patient's ability to:

- Transferring from bed to a chair
  - 0: incapable.
  - 1: needs significant assistance.
  - 2: Needs minimal assistance.

3: Independent.

- Level of mobility of the patient:

0: Immobile.

1: Independent with the help of a wheelchair.

2: Use walking aids or walk with the help of a person.

3: Independent.

This scale is administered at 6 weeks, 4 months and 1 year.

- **Quality of life analysis: EQ-5D-5L questionnaire (ANNEX IV) (48).**

It is a self-administered questionnaire divided into two parts, the descriptive system and the Visual Analogue Scale (VAS).

- The descriptive system EQ-5D-5L. describes health status along five dimensions:
  - Mobility.
  - Self-care.
  - Daily activities.
  - Pain/discomfort.
  - Anxiety/depression.

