This programme is divided into 5 phases, each of these phases coincides with a level of the gait assessment scale. Each individual will start at the level assigned by the doctor and will only have access to the videos of the indicated level and the levels below it. As the patient meets the recovery goals, the physician will provide access to the higher level videos. The functional recovery plan begins the day after the hip fracture and continues after the patient has been discharged for a total of 16 weeks.

- The therapeutic plan for the historical control group (standard practice until 31 December 2020) consisting of postural changes described in the standardised nursing care plan. Within this plan, the patient was moved to a sitting position prematurely (within the first 24 hours) and started to ambulate within the following 48

hours, provided that the patient's general condition allowed it. This group did not receive any specific functional recovery plan.

- The patient is discharged from hospital and will be assigned a link where he/she will be able to access the online platform to send information from the questionnaires sent during the established periods of 1, 3, 6 and 12 months and will also be sent videos illustrating the rehabilitation exercises that he/she will have to perform during this period. The patient and/or carer will be explained how the tool works, how to access the digital information content and how to access the questionnaires. A means of contact will be provided to resolve doubts, if any. The PI will have access through the web/app platform to a control panel where he/she will be able to detect a patient's lack of adherence, if any, or alerts related to clinical evolution, allowing for exhaustive monitoring of the patient.
- Analysis of results: The data collected will be analysed with the SPSS programme. The mean, median and standard deviation of each of the variables will be calculated. Based on the data obtained from the existing literature(31), having selected a sample of 67 patients, a normal distribution can be assumed for all variables  
For baseline demographic and clinical characteristics, a comparison of means for quantitative variables (t-Student), and of proportions (Chi-square) for qualitative will be performed  
The statistical analysis will be carried out with a confidence level of 95%, so that statistically significant values will be considered to be those whose probability is < 0.05.

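### Falls and complications are scheduled only at 6 weeks, 4 months and 1 year, not at the existing 1-, 3- and 6-month app contacts, so falls risk under-reporting and late alerts

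*Combined protocol and SAP*

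**What the plan says.** **Collection of events.** The adverse-event list under Monitoring of adverse events codes falls, pneumonia, new fractures, dementia, infarction, embolism, thrombosis and death. Its timing line reads "This scale is administered at 6 weeks, 4 months and 1 year". Table III agrees in its row "Medical complications (ad hoc questionnaires". The Sampling section counts the visits from discharge: "at 6 weeks, 4 months and 12 after discharge".

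**Programme.** Under Description of the process, the recovery plan starts the day after the fracture and "continues after the patient has been discharged for a total of 16 weeks".

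**App contacts.** The Variables section adds contacts "at discharge, one month after discharge, three months, six months and one year, by means of a digital application". At the post-discharge app times, Table III places only the Oxford Hip Score and the EQ-5D-5L.

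**Alerts.** Data collection procedure gives the clinician a panel with "risk alerts generated by the system based on the data collected and the clinical rules established for this purpose" and says the app shows the patient's state as it develops. Description of the process refers to "alerts related to clinical evolution, allowing for exhaustive monitoring of the patient".

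**Objective and comparator.** Specific objectives includes the programme's effect on preventing falls. The introduction to the second group of variables says that these variables can be measured only in the 2021 cohort, which the protocol calls unexposed.

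**The concern.** Much of the programme is carried out at home by people over 65, some of whom take part through a caregiver because of cognitive impairment. Falls are both an outcome named in the objectives and a plausible harm of exercise. Yet a single scheduled enquiry about them falls while the programme runs, and two thirds of the year rests on one later recall.

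Three contacts that already exist (1, 3 and 6 months) do not ask. Nothing else in the documents fills the gap:

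- No falls diary or event-driven report is described.
- The falls item in STRATIFY concerns hospitalisation.
- The SARC-F falls item (Annex II) looks back over a year, so at 6 weeks and 4 months it also covers time before the fracture. Its answers are graded, not counted or dated.

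At stake are the completeness of the 2021 cohort's falls rate, the ability to place events within or after the programme, and whether the monitoring is as prompt as the protocol describes.

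**Working it through.** The plan states no figure to reproduce here; the check is calendar arithmetic.

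**Inputs.** Visits at 6 weeks, 4 months and 1 year from discharge (Sampling, Table III); app contacts at 1, 3, 6 and 12 months (Variables, Table III); programme of 16 weeks (Description of the process). Assumption: 1 month = 365.25 / 12 = 30.4 days.

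**Step 1. Programme end against visits.** 16 × 7 = 112 days. The visits fall at 6 × 7 = 42, 4 × 30.4 ≈ 122 and 365 days. Only day 42 is at or before day 112; the 4-month visit is 122 − 112 = 10 days after it.

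**Step 2. Sensitivity to the time origin.** If the 16 weeks start 7 or 14 days before discharge (assumed values), the 4-month visit is 17 or 24 days after the end. With 28-day months, 4 months is day 112 and coincides with week 16. If visits were counted from surgery but the 16 weeks from discharge, a stay of more than 10 days would put the 4-month visit inside the programme. The Sampling section counts visits from discharge, so that mix is not what the plan says.

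**Step 3. Recall windows now.** 42 days; 122 − 42 = 80 days; 365 − 122 = 243 days (243 / 365 = 67% of the year). Of the 80 days in the second window, 112 − 42 = 70 are programme time and 10 are not.

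**Step 4. Windows with the app contacts added.** Assessments at about days 30, 42, 91, 122, 183 and 365 give gaps of 30, 12, 49, 31, 61 and 182 days. Those within 112 days are at days 30, 42 and 91, so the count rises from 1 to 3. It stays at 3 if the programme starts up to 112 − 91 = 21 days before discharge.

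**Step 5. Mean recall interval.** If events are spread evenly over the year (an assumption; no rates are given), the mean is Σ gap² / (2 × 365).

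| Schedule | Calculation | Mean recall | Longest recall | Assessments within 16 weeks |
|---|---|---|---|---|
| Current | (42² + 80² + 243²) / 730 = 67,213 / 730 | 92 days (3.0 months) | 243 days | 1 |
| With app items | (30² + 12² + 49² + 31² + 61² + 182²) / 730 = 41,251 / 730 | 57 days (1.9 months) | 182 days | 3 |

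**Step 6. Alerts.** Alerts are built from collected data, and researchers enter visit findings in the same app. On the current schedule, an event just after the 6-week visit could wait up to about 80 days to be entered, and one just after the 4-month visit up to about 243 days.

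**The case against.** The strongest reply is that the schedule is reasonable for an observational study of routine care. The in-person visits follow the unit's own protocol and functional recovery is the overall objective. The 4-month visit asks about everything since week 6, so it covers the rest of the programme. Its position outside the programme rests on about 10 days with no visit windows stated. Most of the coded events are serious and unlikely to be forgotten. Patients whose impairment prevents use of the app are excluded unless accompanied. All of this stands. It confines the recall problem largely to falls, but does not explain why contacts already being made leave the question out.

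Three stronger readings are tempting, and the documents do not support them:

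- **That events are lost.** No event or recall rates are given. Under-reporting is a risk, not a demonstrated loss.
- **That events cannot trigger alerts.** Visit data reach the app, so they can do so late. A poor Oxford Hip Score or EQ-5D-5L answer might also raise an alert. The rules are not described, and the promise concerns adherence and clinical course, not each fall.
- **That under-recall flatters the programme against 2020.** These variables have no 2020 counterpart. Missed falls would lower a single-cohort rate; they would not bias a between-cohort contrast. The missing comparator is itself the larger limit on the falls objective.

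It is also fair that recording dates at the existing visits would already separate programme from post-programme events, and that the remedy leaves half the year on one recall. App adherence is a limitation that the protocol acknowledges.

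**Conclusion.** The point holds as a gap in scheduling. Falls and complications have three assessments, of which one lies inside the 16-week programme, and the last two are about 8 months apart. The intervening app contacts do not ask about them. Falls are the events most at risk of under-reporting, and reports of any event between visits would reach the panel with a delay of up to about 243 days.

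This rests on visits counted from discharge, as the Sampling section states, and on calendar months. The direction is clear, but the number of events missed cannot be estimated from the documents. The change is a worthwhile, inexpensive improvement to event ascertainment; it does not bear on the comparison of functional recovery between cohorts.

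**What to change.** 1. Add the existing falls and complications items, with the date of each event, to the app questionnaires at 1, 3 and 6 months, answered by the patient or caregiver. The 12-month contact coincides with the 1-year visit and needs no addition.
2. Make the answers available to the existing control panel, and state which answers raise an alert and who reads it.
3. Keep collection at the three visits as confirmation. Record dates there too, and remove duplicates by matching event type and date.
4. Report events separately for the 16-week programme and the time after it, as a description of the 2021 cohort, and state the time origin of both the programme and the visits.

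**Cost.** A few items on forms already sent, with no extra visit. There is slightly more response burden in an elderly group, some work to reconcile app and visit reports (the 1-month contact comes about 12 days before the 6-week visit), and time for someone to read the alerts. A recall of about 182 days between 6 and 12 months remains and should be acknowledged as a limitation.

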### **Limitations of the study**

The project poses a number of constraints that need to be taken into consideration:

- The current pandemic situation affecting the hip fracture care process.

- The necessary involvement of the relative or the residence in the therapeutic process.
- Adherence to the application for data collection from the patient's experience.
- The use of a mobile application for data collection and the implementation of the recovery programme in an ageing population. A specific follow-up will be established by the research team to support participants who present any kind of difficulty.
- Thosederived from an observational study, which is not conducted under the control and randomisation conditions of a clinical trial

## WORK PLAN (ANNEX V)

This research project is intended to be carried out in the Functional Recovery Unit integrated in the Orthogeriatrics Service of the HSJD and has the following work plan:

- **Administrative Phase.**

Complete development of the project in writing and submission for approval to the Doctoral Commission of the University of Murcia and the Research Commission of the Order of San Juan de Dios. Once the project has been approved, it will be submitted to the Clinical Research Ethics Committee (CEIC) as deemed appropriate.

- **Initial Phase-Start-up. Duration 18 months.**

The programme will start when the patient is admitted to hospital for hip fracture. Participants who meet the eligibility criteria for the study will be recruited and data collected. Participants will be informed of the purpose of the study (Annex VI) and their written informed consent will be requested (Annex VII).

**Description of the process:**

- Candidate selection: the patient will be cared for by orthogeriatrics unit according to its standard clinical practice protocol approved by the medical management, and based on the care model established by the National Hip Fracture Registry.
- If the patient is admitted from the emergency department, a referral to geriatrics will be requested to assess the patient.
- Explanation of the programme and request for informed consent (Annexes VI and VII): at the time of admission, an interview will be held between the patient or relative and the doctor in charge (traumatology service) explaining the process for patients with osteoporotic hip fracture in the Hospital; which encompasses the set of coordinated medical decisions (Emergency, Traumatology, Geriatrics) with the aim of obtaining the highest quality care, shorter hospital stay with the maximum level of independence and avoiding a second fracture. In the same way and at the same time, the multimodal plan of therapeutic exercise and functional recovery that will help them during their recovery process will be explained to them.

Subsequently, the patient will be informed of the data collection process, mobile application and follow-up for 1 year, and signatures will be requested for informed consent for anaesthesia, surgery and participation in the study. If the patient accepts, Caaring® application.

Profiles of patients whose clinical circumstances permit, a corroborated history should be taken, including:

- Premorbid function and mobility.
- Available social support (including whether the patient already has a caregiver or whether someone is willing and able to provide such support)
- Relevant current clinical conditions
- State of mind.
- Hip Surgery.
- Recovery programme (protocol of action that replaces the usual practice developed previously):
  - Specific hip fracture recovery programme, restoring the mobility, strength and balance of the operated patient, in order to facilitate the return to a functional state as close as possible to the state prior to surgery and in the shortest possible time, as detailed in Annex VIII. This programme is part of the standard treatment protocol implemented since January 2021 by the Orthogeriatrics Unit of the HSJD.

This programme is divided into 5 phases, each of these phases coincides with a level of the gait assessment scale. Each individual will start at the level assigned by the doctor and will only have access to the videos of the indicated level and the levels below it. As the patient meets the recovery goals, the physician will provide access to the higher level videos. The functional recovery plan begins the day after the hip fracture and continues after the patient has been discharged for a total of 16 weeks.

- The therapeutic plan for the historical control group (standard practice until 31 December 2020) consisting of postural changes described in the standardised nursing care plan. Within this plan, the patient was moved to a sitting position prematurely (within the first 24 hours) and started to ambulate within the following 48

hours, provided that the patient's general condition allowed it. This group did not receive any specific functional recovery plan.

- The patient is discharged from hospital and will be assigned a link where he/she will be able to access the online platform to send information from the questionnaires sent during the established periods of 1, 3, 6 and 12 months and will also be sent videos illustrating the rehabilitation exercises that he/she will have to perform during this period. The patient and/or carer will be explained how the tool works, how to access the digital information content and how to access the questionnaires. A means of contact will be provided to resolve doubts, if any. The PI will have access through the web/app platform to a control panel where he/she will be able to detect a patient's lack of adherence, if any, or alerts related to clinical evolution, allowing for exhaustive monitoring of the patient.
- Analysis of results: The data collected will be analysed with the SPSS programme. The mean, median and standard deviation of each of the variables will be calculated. Based on the data obtained from the existing literature(31), having selected a sample of 67 patients, a normal distribution can be assumed for all variables  
For baseline demographic and clinical characteristics, a comparison of means for quantitative variables (t-Student), and of proportions (Chi-square) for qualitative will be performed  
The statistical analysis will be carried out with a confidence level of 95%, so that statistically significant values will be considered to be those whose probability is < 0.05.
- Dissemination of results: the results of this study will be presented for dissemination in scientific journals and specialised conferences.

